### **2.2.2. Safety Endpoints**

The safety endpoints of this study include the following and will be conducted:

- Adverse events (AEs)
- Local tolerability assessments
- Clinical laboratory parameters
- Vital signs

- Physical examinations
- 12-lead electrocardiograms (ECGs)
- Prior and concomitant medications

### 3. Overall Study Design and Plan

This is a 24-week, parallel group, double blind, vehicle-controlled study for the treatment of subjects with non-segmental facial vitiligo. This study was planned to include both male and female adults having a facial BSA  $\geq 0.25\%$  and F-VASI  $\geq 0.25$ . A total of 500 subjects were planned to be randomized. After having met all inclusion criteria, and none of the exclusion criteria, subjects were to be randomized in a 3:3:3:1 ratio as mentioned below in Section 3.4. Screening for up to 5 weeks followed by 24 weeks of treatment phase was planned for this study. In addition to the study drug ARQ-252 cream and vehicle cream, subjects were randomized to receive Daavlin series NB-UVB active or sham units. Subjects have to record the date and time each dose has been applied, any missed doses, and any additional comments. There was a follow-up visit approximately 1 week after treatment has been completed.

Upon the sponsor discretion, this study was terminated and none of the subjects could finish the entire treatment period. All the subjects that were currently enrolled have been early terminated and subjects that are in screening have been screen failed. Emergency unblinding was performed after following Premier Research SOPs.

#### 3.1. Overall Design

#### 3.2. Sample Size and Power

The primary statistical comparisons will be to compare

- ARQ-252 cream 0.3% in combination with phototherapy vs. vehicle cream in combination with NB-UVB.
- ARQ-252 cream 0.3% in combination with phototherapy vs. ARQ-252 cream 0.3% in combination with sham phototherapy at the 5% significance level.

A sample size of 500 subjects was planned to provide approximately 84% power to detect an ARQ-252 cream 0.3% in combination with phototherapy response rate of at least 50% vs. a vehicle cream in combination with phototherapy response rate of 30%, and approximately 84% power to detect an ARQ-252 cream 0.3% in combination with phototherapy rate of at least 50% vs. an ARQ-252 cream 0.3% in combination with sham phototherapy rate of 30%, using a stratified Cochran-Mantel-Haenszel test conducted at the 0.025 alpha level for each comparison. A drop out rate of 15% at 24 weeks was assumed.

Upon successful testing for the comparisons above, a hierarchical testing scheme will be used to test the following secondary comparisons:

- ARQ-252 cream 0.3% in combination with phototherapy vs. vehicle cream BID in combination with the sham phototherapy.

- ARQ-252 cream 0.3% in combination with sham phototherapy vs. vehicle cream BID in combination with the sham phototherapy.
- Vehicle cream BID in combination with phototherapy vs. vehicle cream BID in combination with the sham phototherapy.

Assuming a vehicle cream BID in combination with the sham phototherapy rate of no more than 5%, these comparisons are expected to have at least 74% power. These comparisons will be made at either the 0.025 or 0.05 level, depending on the outcome of the primary statistical comparisons.

### **3.3. Study Population**

The study population consists of male and female adults (>18 y/o) with facial non-segmental vitiligo having F-BSA  $\geq$  0.25% and F-VASI  $\geq$  0.25, with a maximum BSA (total body inclusive of the face, whether or not in areas to be treated in this study) of 15%.

### **3.4. Treatments Administered**

Subjects who meet the eligibility criteria will be randomized to 1 of the 4 following treatment groups in a 3:3:3:1 ratio:

- ARQ-252 cream 0.3% BID with NB-UVB phototherapy
- ARQ-252 cream 0.3% BID with sham NB-UVB phototherapy
- Vehicle cream BID with NB-UVB phototherapy
- Vehicle cream BID with sham NB-UVB phototherapy

### **3.5. Method of Assigning Subjects to Treatment Groups**

Subjects will be randomized and assigned to treatment arm in a 3:3:3:1 ratio according to a computer-generated randomization list. Randomization will be stratified by study site and FitzPatrick skin type (I-III or IV-VI), with at least 50% of subjects having Fitzpatrick skin type IV-VI.

### **3.6. Blinding and Unblinding**

The study was planned to be double-blinded, therefore neither the subjects nor the Investigator, Independent Rater, or clinical site personnel were aware of which investigational product (ARQ- 252 0.3% cream or vehicle cream) or NB-UVB phototherapy unit (Active or Sham) the subject receives. However, upon the sponsor discretion, the study was terminated and treatment unblinding was performed following Premier Research SOPs.

### **3.7. Schedule of Events**

A detailed schedule of events for the study is provided in [Table 1](#).

**Table 1: Schedule of Events**

Study Procedure	Screen	Baseline Day 1	Wk 4 Day 29	Wk 8 Day 57	Wk 12 Day 85	Wk 16 Day 113	Wk 20 Day 141	Wk 24 Day 169	Wk 25 Day 176
Visit	1	2	3	4	5	6	7	8	9
Visit Window	-35 days		+/- 5 days	+/- 5 days	+/- 5 days	+/- 5 days	+/- 5 days	+/- 7 days	+/- 7 days
Informed consent	X								
Demographics	X								
Fitzpatrick skin type assessment	X								
Medical and surgical history	X								
Physical examination a	X	X			X				X
Vital signs, height, weight b	X	X	X	X	X	X	X	X	X
I/E criteria	X	X							
Randomization		X							
Hematology, Serum Chemistries, UA, TSH/T4	X	X	X		X			X	
Lipid (Fasting) c		X						X	
Resting 12-lead ECG	X		X		X			X	
BSA d (Full Body), T-VASI e	X	X			X			X	
F-BSA d , F/N-BSA d , BSA (Hands, Forearms, Elbows) d , F-VASI e , F/N-VASI e , FOREARM-VASI e , HAND-VASI e , FsIGA f	X	X	X	X	X	X	X	X	X
VNS g , PaGIC-V h			X	X	X	X	X	X	
VitiQoL i		X	X	X	X	X	X	X	
Local Tolerability Assessments j		X	X	X	X	X	X	X	
Digital Photography k		X	X	X	X	X	X	X	
Urine pregnancy test l		X	X	X	X	X	X	X	X
Serum pregnancy test m	X								

AD-ST-33.06 Effective date: 12-Nov-2020

Study Procedure	Screen	Baseline Day 1	Wk 4 Day 29	Wk 8 Day 57	Wk 12 Day 85	Wk 16 Day 113	Wk 20 Day 141	Wk 24 Day 169	Wk 25 Day 176
Visit	1	2	3	4	5	6	7	8	9
Visit Window	-35 days		+/- 5 days	+/- 5 days	+/- 5 days	+/- 5 days	+/- 5 days	+/- 7 days	+/- 7 days
Follicle-StimulatingHormone (FSH) a	X								
PK Sampling b		X	X		X			X	
NB-UVB Phototherapy inclinic c		X							
Return of USB stick to sitefor phototherapy data uploading d			X	X	X	X	X	X	
Dispense IP kit e		X	X	X	X	X	X		
IP application in clinic f		X	X	X	X	X	X		
Dispense/review diary		X	X	X	X	X	X		
Weigh IP tubes g		X	X	X	X	X	X	X	
Compliance calculation h			X	X	X	X	X	X	
Adverse event assessment i	X	X	X	X	X	X	X	X	X
Concomitant medications	X	X	X	X	X	X	X	X	X

a Limited physical examination: skin, lungs, and heart only

b Height will be measured at Baseline only. Weight will be collected at screening, baseline and Week 24.

c Fasting required for a minimum of 8 hours prior to blood draw

d BSA will utilize the subject's handprint method where 1 handprint will approximate 1% of the body surface area involved. F-BSA will include the % BSA of non-segmental vitiligo on the face only. F/N-BSA will include the % of BSA of vitiligo on the face and neck area only. Full Body BSA will include the % of BSA of vitiligo on all areas of the body. This assessment will be performed by an independent rater per the protocol.

e Vitiligo Area Scoring Index (VASI) per the protocol: F-VASI will utilize measuring only the face. "Face" is defined as including the area on the forehead to the original hairline, on the check to the jawline vertically to the jawline and laterally from the corner of the mouth to the tragus. The area "face" will not include surface areas of lips, scalp, ears, or neck but will include the eyelids and nose. F/N-VASI will utilize VASI measuring the face and neck as defined by the Face as defined above in addition to the neck area. FOREARM-VASI will include scoring of the forearms and elbows. HAND-VASI will include scoring of the hands only. T-VASI will include the following sites: (1) head/neck, (2) hands, (3) upper extremities (excluding hands), (4) trunk, (5) lower extremities (excluding feet), and (6) feet. All VASI assessments will be performed by an independent rater per the protocol.

f The Facial Static Investigator Global Assessment (FsIGA) is a global score of vitiligo severity for the face only. The outcome measure incorporates location, distribution, size, depigmentation within lesions and presence or absence of signs of activity. Examination of skin should be performed with both normal lighting and Woods lamp. This assessment will be performed by an independent rater per the protocol.

g Vitiligo Noticeability Scale (VNS) is a 5-point scale which compares vitiligo from before treatment to how

noticeable is the vitiligo at the time of the assessment. The VNS will be completed by subjects with respect to vitiligo on the facial target patch. The target patch on the face is selected by the subject as being the patch that they would most like to see in an improvement in. The photos taken on the facial target patch at the Baseline visit prior to treatment and at the subsequent visits will be used as reference to assess the change.

- h The Patient Global Impression of Change-Vitiligo (PaGIC-V) is a 7-point scale on which the subject will rate improvement compared to baseline and will be evaluated for the face only.
- i The Vitiligo Quality of Life (VitiQoL) is a 16-item questionnaire with a 7-point numerical scale from (0 - Not at all) to (6 - All of the time). The VitiQoL is completed by the subject.
- j Tolerability assessments should be recorded prior to study drug application for Investigator assessment and 10-15 minutes post-drug application for subject ('0-3' burning/stinging assessment). Investigators will specify if any application site reaction is due, in whole or in part, to the effects of phototherapy treatment. Only the Investigator assessment will take place on Week 24.
- k Digital Photography will be conducted at all sites for all subjects. Required study photos will be taken of the treatment areas during the Baseline Visit. In addition, a photo of the facial target patch will be taken as reference for the VNS assessment. Fixed, multi-angle photos will be taken at select sites for additional evaluation.
- l A urine pregnancy test will be administered to all females of child-bearing potential. A negative result is required for continued participation in the study, and results must be available prior to dispensing of study drug at each visit.
- m Serum pregnancy testing will be performed at Screening; a negative result is required for participation in the study.
- n FSH will be performed (if indicated) at Screening to confirm post-menopausal status.
- o PK samples will be collected from all subjects at Baseline, Week 4, Week 12, and Week 24. The samples will be drawn prior to application of the investigation product in the clinic. Subjects should apply investigational product 11-12 hours before the PK collection time.
- p NB-UVB Phototherapy treatment will occur in the clinic at the Baseline Visit prior to the initial IP application. The treatment will be per the NB-UVB Treatment Protocol and be tailored per the subject's Fitzpatrick Score. The subject will be provided with the phototherapy unit in addition to a USB stick which will be inserted into the unit to obtain phototherapy data during the course of the treatment period.
- q Subjects should be instructed to return the USB stick from the phototherapy unit to site for the uploading of the phototherapy data. Once the data has been uploaded by the site staff, a new USB stick should be provided to the subject to insert into the NB-UVB phototherapy unit.
- r IP kits will be dispensed based on % BSA affected. See IP Handling Manual for details.
- s Subjects to apply assigned IP in clinic at these visits. The time of application will be documented.
- t Each IP tube will be weighed prior to dispensing at the Baseline visit and at each follow-up clinic visit according to the Schedule of Visits and Assessments. When IP is applied in the clinic, the IP tube will be weighed before and after IP application. See IP Handling Manual for details.
- u Compliance calculation is described in the IP Handling Manual.
- v Adverse Events (AEs) and clinically significant abnormal laboratory test value(s) will be evaluated by the PI and treated and/or followed up for up to 30 days after end of treatment or until the symptoms or value(s) return to normal, or acceptable levels, as judged by the PI.

## 4. Statistical Analysis and Reporting

### 4.1. Introduction

Data processing, tabulation of descriptive statistics, calculation of inferential statistics, and graphical representations will primarily use SAS (release 9.4 or higher). If the use of other software is warranted, the final statistical methodology report will detail what software was used for what purposes.

Continuous (quantitative) variable summaries will include the number of subjects (n) with non-missing values, mean, standard deviation (SD), median, Q1, Q3, minimum, and maximum.

Categorical (qualitative) variable summaries will include the frequency and percentage of subjects who are in the particular category or each possible value. In general, the denominator for the percentage calculation will be based upon the total number of subjects in the study population for the treatment group, unless otherwise specified. The denominator for by-visit displays will be the number of subjects in the relevant study population with non-missing data at each visit.

The minimum and maximum will be reported with the same degree of precision (i.e., the same number of decimal places) as the observed data. Measures of location (mean, median, Q1, and Q3) will be reported to 1 degree of precision more than the observed data and measures of spread (SD) will be reported to 2 degrees of precision more than the observed data.

Percentages will be presented to 1 decimal place, unless otherwise specified.

No formal hypothesis testing was done for this study.

### 4.2. Interim Analysis and Data Monitoring

No interim analyses are planned.

## 5. Analysis Populations

The following analysis populations are planned for this study:

- **Safety Population (SAF):** The Safety population includes all subjects who are enrolled and received at least 1 confirmed dose of investigational product (IP). This population will be used for all safety analyses.
- **Intent-To-Treat Population (ITT):** The ITT population includes all randomized subjects in the study. This population will be used for efficacy descriptive summaries along with disposition.
- **Pharmacokinetic Population (PK):** The PK population will include all subjects who are randomized and receive at least 1 application of IP and have at least 1 analyzed PK sample.

## **6. General Issues for Statistical Analysis**

The study was terminated based on sponsor's decision. All the analysis are in descriptive nature. No formal test will be performed.

### **6.1. Statistical Definitions and Algorithms**

#### **6.1.1. Baseline**

For assessments where time was recorded (e.g., ECG), the last observation recorded before the first application of study drug will be used as the baseline observation for all calculations of change from baseline. For assessments where time was not recorded, the last observation recorded on or before the day of first application of study drug will be used as the baseline observation for all calculations of change from baseline.

For subject tolerability assessments, baseline is derived as the last non-missing measurement taken on the day of first application of study drug.

#### **6.1.2. Adjustments for Covariates**

No adjustment for covariates will be made for this study. All the analyses are descriptive, and no subgroup analysis will be performed.

#### **6.1.3. Multiple Comparisons**

No adjustments will be made for multiple comparisons because there will be no formal hypothesis testing, nor any inferential statistical analyses, only descriptive summaries.

#### **6.1.4. Handling of Dropouts or Missing Data**

No inferential statistical analyses are planned for this study.

#### **6.1.5. Analysis Visit Windows**

Safety and efficacy data will not be windowed and will be analyzed as per the nominal visit present in the database.

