## **5.5. Early Termination Visit**

If a subject is withdrawn or wishes to exit the study prior to the final study visit, an early termination visit will be scheduled. This visit should include the procedures and assessments that would be performed at the Week 24 visit as described in the Schedule of Visits and Assessments ([Section 1.3](#)).

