#### **6.1.7. Derived Variables**

- **Weight of IP (g)** = dispensed tube weight – returned tube weight.

- **Number of expected IP applications** = calculated as  $2 * (\text{last treatment date} - \text{first treatment date} + 1)$ .
- **Number of IP applications** = number of expected IP applications – missed IP applications as collected in the case report form (CRF). As the time of missing dose is not captured in the CRF, only the dates will be used in determining number of missed doses; if 2 records exist for the same date, that will be considered as 2 missed IP applications.
- **Days on IP** = Calculated as last treatment date – first treatment date + 1. For subjects who are missing the date of last study drug application, for any reason, the last known contact date from subject visits CRF will be used in the calculation of treatment duration.
- **BMI (kg/m2)** =  $(\text{weight in kg}) / [(\text{height in cm}/100)^2]$ . For all visits, baseline height will be used to derive BMI since height is collected only at baseline.
- **Change from baseline** = value at current time point – value at baseline.
- **Percent change from baseline** =  $(\text{value at current time point} - \text{value at baseline}) / \text{value at baseline}$ .
- **TEAE** = any AE with an onset date/time after the first application of IP. If time is unavailable, any AE occurring on or after the date of first application of IP will be considered treatment emergent.

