#### 6.1.8. Data Adjustments/Handling/Conventions

Upon the sponsor discretion, only safety and limited efficacy will be presented in Clinical Data Interchange Standards Consortium (CDISC) datasets. Data not subject to analysis according to this plan will not appear in any tables or graphs or listings or the CDISC datasets.

Adverse events will be coded using the Medical Dictionary for Regulatory Activities (MedDRA) version 23.1 thesaurus.

A treatment-related AE to study drug is any AE with a relationship to the study drug of possibly, probably, likely, or missing.

A treatment-related AE to phototherapy treatment is any AE with a relationship to the phototherapy treatment of likely or missing.

For partial AE and medication start dates:

- If the year is unknown, then do not impute the date but assign a missing value.
- If the year is known, but the month or month and day is unknown, then:
  - If the year matches the year of first dose date and the end date (if present) is after first dose date, then impute as the month and day of the first dose date.

- Otherwise, assign 01 January.
- If the year and month are known, but the day is unknown, then:
  - If the month and year match the month and year of the first dose date, then impute as the day of the first dose date.
  - Otherwise, assign 01.

For partial AE and medication end dates:

- If the year is unknown, then do not impute the date but assign as missing value.
- If the year is known, but the month or month and day is unknown, then:
  - If the year matches the year of the last date of the study (date of last contact if subject lost to follow-up; date of completion or early termination otherwise), then impute as the month and day of the last date of the study.
  - Otherwise, assign 31 December.
- If the year and month are known, but the day is unknown, then:
  - If the month and year match the month and year of the last date of the study, then impute as the day of the last date of the study.
  - Otherwise, assign the last day of the month.

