## **8. Efficacy Analysis**

Due to the study termination, it was the sponsor decision to not execute any efficacy analyses. Though the protocol indicates primary and secondary endpoints, upon the sponsor decision only F-VASI summaries will be provided based on observed value. Hence, observed, change and percent change from baseline in F-VASI scores will be summarized descriptively by treatment group using ITT population.

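### Does the SAP need a display rule for Early Termination records, given that all enrolled subjects were stopped early?

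*SAP*

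**What the plan says.** SAP 6.1.5 has a single visit rule: "Safety and efficacy data will not be windowed and will be analyzed as per the nominal visit present in the database". SAP 4.1 adds: "The denominator for by-visit displays will be the number of subjects in the relevant study population with non-missing data at each visit".

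SAP Section 3 describes the sponsor's stop: "All the subjects that were currently enrolled have been early terminated". It also says that no subject completed treatment. Protocol 5.5 provides an ET visit for anyone who leaves before the final visit: "This visit should include the procedures and assessments that would be performed at the Week 24 visit".

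On output, SAP Section 8 keeps one efficacy variable: "Hence, observed, change and percent change from baseline in F-VASI scores will be summarized descriptively by treatment group using ITT population". SAP 9.3 to 9.5 summarize laboratory tests, vital signs (with weight and BMI) and ECGs by study visit. For BMI, SAP 6.1.7 says: "For all visits, baseline height will be used to derive BMI since height is collected only at baseline". Footnote b of SAP Table 1 limits weight: "Weight will be collected at screening, baseline and Week 24". SAP 6.1.8 closes its opening paragraph with: "Data not subject to analysis according to this plan will not appear in any tables or graphs or listings or the CDISC datasets".

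**The concern.** The SAP was written after the stop, so ET is the planned last assessment for the whole enrolled population. Yet SAP Table 1 runs from Screening to Week 25 with no ET column. SAP 6.1.4, on dropouts, says only that nothing inferential is planned. Section 8 names no visit for F-VASI. A literal reader could combine the missing column with the exclusion in 6.1.8 and conclude that ET values have no row and no listing.

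On that reading the report would lose each subject's last F-VASI, laboratory, ECG and vital-sign values, and essentially all post-baseline weight and BMI. A milder worry is that ET values might appear as Week 24, because the two visits share their procedures. That would overstate exposure in a trial where nobody completed treatment.

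**Working it through.** The plan gives no figure on this point to reproduce. The check is a count from the schedule and a comparison of sections.

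**1. What depends on ET.** SAP Table 1 has 7 post-baseline visits (Weeks 4, 8, 12, 16, 20, 24, 25). Removing Weeks 24 and 25 leaves 7 − 2 = 5 before Week 24.

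| Assessment | Scheduled before Week 24 | Count |
|---|---|---|
| F-VASI | Weeks 4, 8, 12, 16, 20 | 5 |
| Blood pressure, heart rate, temperature | Weeks 4, 8, 12, 16, 20 | 5 |
| Laboratory tests | Weeks 4, 12 | 2 |
| ECG | Weeks 4, 12 | 2 |
| Fasting lipids | none | 0 |
| Weight, hence BMI | none (footnote b) | 0 |

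Weight falls at 1 of the 7 post-baseline visits (Week 24) and at 0 of the 5 before it. For subjects stopped before Week 24, every planned post-baseline weight is therefore an ET value. The wording has to be essentially all rather than all, because an off-schedule weight, or a Week 24 visit held early in its window of ±7 days, cannot be excluded. For the other measures, the share of subjects whose only post-baseline value is the ET value depends on how long each was treated. The documents do not report that, so no share is given.

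**2. Does 6.1.5 reach ET records?** Its subject is safety and efficacy data without exception, and its key is the visit label in the database. It does not refer to the columns of Table 1. That table repeats the protocol's schedule (Protocol 1.3), which also has no ET column even though Protocol 5.5 creates the visit in its text. SAP Section 1 says that operational details of timing are not repeated unless they matter to the analysis. A missing column in a schedule grid is therefore no sign that ET is excluded.

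**3. Does 6.1.8 remove them?** The sentence before the exclusion confines the datasets to safety and a limited part of efficacy. In that setting the exclusion covers endpoints abandoned after the stop, such as VNS or VitiQoL. F-VASI (SAP Section 8) and safety data (SAP Section 9) are subject to analysis, so it does not touch their ET values.

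**4. What happens under each possible label?**

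- *ET has its own label.* The rule gives an ET row. Nothing is lost or mistimed, and the weight and BMI change tables get their post-baseline row.
- *ET is stored as Week 24.* The values are shown, but under a name that overstates exposure. SAP Section 3 states that nobody finished treatment, and SAP 7.3 summarizes days on investigational product by arm.
- *ET is left out.* This would depart from 6.1.5, and it would show: continuous summaries report n (SAP 4.1), disposition reports numbers randomized and treated (SAP 7.1), and weight and BMI change tables would have almost no post-baseline entries.

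**5. BMI.** The instruction in 6.1.7 fixes which height to use. It does not say that weight is measured at every visit, so it does not contradict footnote b. Since ET repeats the Week 24 procedures, it includes weight, and SAP 9.4 can be carried out.

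**The case for a change.** The strongest case for a change is that the authors knew every enrolled subject had stopped early and still did not name the visit this produces. Two programmers could follow the text and build different tables. Treatment was already unblinded, so it is better to settle wording before any summary is run. A sentence would cost almost nothing.

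Part of this stands. The SAP has no rule naming ET, the database label is unknown, and storage as Week 24 cannot be ruled out. But SAP Section 10 says that table shells were developed with the SAP, and shells are a usual place to fix row labels. The choice of label applies to all arms alike, so knowing the allocation gives little room to favor one of them.

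A fuller rule would bring its own problems. Letting an ET value count as Week 24 only on Days 162 to 176 (169 ± 7) would be a study-day window, which 6.1.5 rules out. It would also leave a value in that range eligible for two rows. Printing days on product, or days since last application, beside an ET row is a layout preference: SAP 7.3 already gives days on product by arm. An ET row would pool unequal exposures and could not show a time trend however it was annotated.

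**Conclusion.** No change is needed. The facts behind the concern are correct: ET is not named, and planned post-baseline weight and BMI come essentially only from it. The harm, however, requires reading 6.1.5 as if it referred to the Table 1 columns, and 6.1.8 as if it covered data that Sections 8 and 9 plan to analyze. Followed as written, the SAP yields sound descriptive tables by nominal visit, with ET as one of those visits.

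The gap is one of detail that analysts or the shells would fill sensibly. Its effect on inference is nil, since no hypothesis test is planned, and values at scheduled visits keep their true week. The conclusion assumes that the database or the shells identify ET as a visit of its own. If ET were stored as Week 24, the values would still be reported, and the cost would be a misleading row name in a report that states elsewhere that no subject completed treatment.
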